3 TRIAL DESIGN

This is a non-randomised open label, single dose level Phase II study in two patient groups (CML and AML) based on HLA A2 genotype. Consented and eligible HLA A2+ patients will be vaccinated with two DNA vaccines, p.DOM-WT1-37 (epitope sequence: VLDFAPPGA) and p.DOM-WT1-126 (epitope sequence: RMFPNAPYL). Patients with HLA A2-ve genotype will therefore form the unvaccinated control group. The sample size for the HLA A2+ group has been determined using a A'Hern's single stage study design.

Intervention group of HLA A2+ patients:

32 HLA A2 +ve patients with data to at least 16 weeks will be recruited into the CML treatment group.39 HLA A2 +ve patients with data to at least 16 weeks will be recruited into the AML treatment group.

Control groups of HLA A2-negative but otherwise eligible, consenting patients:

CML: Control group: all eligible and consenting patients who are HLA A2 negative AML: Control group: all eligible and consenting patients who are HLA A2 negative

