Title:	WT1 Immunity via DNA fusion Gene Vaccination in Haematological Malignancies by intramuscular injection followed by intramuscular electroporation.
Sponsor:	University Hospital Southampton NHS Foundation Trust
Sponsor Ref Number:	RHMCAN0700
Funder:	Leukaemia & Lymphoma Research, and the Efficacy and Mechanism Evaluation (EME) programme.
Trial Phase:	II
Indication:	Chronic Myeloid Leukaemia (CML) and Acute Myeloid Leukaemia (AML)
Primary Objective:	CML: Molecular response of BCR-ABL. AML: Time to disease progression.
Secondary Objective:	Molecular response of WT1 transcript levels, immune responses to WT1 and DOM, Toxicity, CML-Time to disease progression, next treatment and survival, AML-2 year survival, overall survival
Trial Design:	Open label, single dose level, Phase II study in two patient groups (CML and AML) using genetic randomisation. Consented and eligible HLA A2+ve patients will be vaccinated with two DNA vaccines. HLA A2 –ve patients will be followed up on trial without vaccination.
Sample size : (split by treatment group)	Vaccination Arm (HLA A2+ve patients): 32 patients with data to at least 8 weeks will be recruited into the CML treatment group. 39 patients with data to at least 8 weeks will be recruited into the AML treatment group. Control Arm: this arm will consist of all eligible and consenting patients who are HLA A2 –ve.
Main inclusion Criteria:	CML: Philadelphia chromosome positive CML in chronic phase, in complete cytogenetic response (CCyR) but with detectable BCR-ABL transcripts and maintained the CCyR on tyrosine kinase inhibitor (TKI) monotherapy for a minimum of 24 months. AML: WT1 ⁺ AML in CR or morphologic CR with incomplete blood count recovery (CRi).
Main exclusion Criteria:	CML: accelerated phase or blast crisis or having achieved CMR at any point during tyrosine kinase inhibitor therapy. Tyrosine kinase inhibitor dose modification in the previous year or interruption for > 15 days in the previous 6 months prior to recruitment.
Investigational Products:	p.DOM-WT1-37 DNA Vaccine p.DOM-WT1-126 DNA Vaccine

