3.1 PATIENT EVALUABILITY AND REPLACEMENT

Where patients do not fulfil the necessary criteria to be eligible for analysis (as set out in Section 10.2) additional patients may be recruited in their place.

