10 STATISTICS AND DATA ANALYSIS

10.1 SAMPLE SIZE CALCULATION

10.1.1 SAMPLE SIZE CALCULATION FOR CML

The sample size calculation is based on A'Hern's Single-Stage Design and the primary outcome measure of molecular response (BCR-ABL or WT1).

A molecular response (BCR-ABL or WT1) rate of 20% would imply the vaccine clearly warrants further investigation. A molecular response rate of 5% or less would be unacceptable and would indicate the vaccine does not warrant further investigation. The probability of obtaining a false positive result, α (i.e. incorrectly accepting for further study a treatment that has a true PFS rate 30%) is set at 10%. The probability of a false negative result, β (i.e. incorrectly rejecting for further study a treatment with a true PFS rate of 50%) is set at 10%. Using these parameters, $\alpha = 0.1$, $\beta=0.1$, p0=5%, p1=20%, 32 HLA A2+ve patients need to be recruited to the study. The drop-out rate is expected to be less than 10%, hence a total of 36 patients will be recruited.

This trial needs to observe a minimum of 4 out of 32 patients who are molecular responders in order to provide evidence that the vaccine warrants further investigation. Patients will be followed up for 2 years to assess molecular response.

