10.1.2 SAMPLE SIZE CALCULATION FOR AML

The sample size calculation is based on A'Hern's Single-Stage Design and the primary outcome measure of progression free survival (PFS) at 2 years.

A progression free survival rate of 50% at 2 years would imply the vaccine clearly warrants further investigation. A PFS rate of 30% or less at 2 years would be unacceptable and would indicate the vaccine does not warrant further investigation. The probability of obtaining a false positive result, α (i.e. incorrectly accepting for further study a treatment that has a true PFS rate 30%) is set at 10%. The probability of a false negative result, β (i.e. incorrectly rejecting for further study a treatment with a true PFS rate of 50%) is set at 10%. Using these parameters, $\alpha = 0.1$, $\beta=0.1$, p0=30%, p1=50%, 39 HLA A2+ve patients need to be recruited to the study. The drop-out rate is expected to be less than 10% (see section 3.1 for details of patient replacement).

This trial needs to observe a minimum of 16 out of 39 patients who are progression free and alive at 2 years in order to provide evidence that the vaccine warrants further investigation.

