10.2 ANALYSIS PLAN

Molecular Analysis

The analyses on molecular response will be performed on all patients with molecular data at a minimum of 2 post-baseline time points (HLA A2 positive patients must also have received at least 1 dose of the vaccine).

Immunological Analysis

To be evaluable for immunological response, positive HLA A2 patients must receive at least 1 dose of the vaccine and the immunological testing must be available until at least week 8 post first dose.

Safety Analysis

For safety analyses, all patients with positive HLA A2 status who received at least one study drug administration will be evaluable for toxicity. All controls will be included in the safety analyses, where relevant.

Other Analysis

For all other analyses, an intention to treat principle will be used.

10.2.1 ANALYSIS FOR CML PATIENTS ONLY:

Primary:

The primary endpoint is molecular response of BCR-ABL (major or minor response or CMR). For the purpose of analysis, response (as defined by section 9.6) will be measured at weeks 4, 8, 12, 16, 20, 32 and 11, 17 and 23 months. Fisher's exact test will be used to compare differences in proportions of molecular response in CML patients versus controls.

Secondary:

The primary analysis will be repeated for major response or CMR of BCR-ABL.

The analysis methods used for BCR-ABL will be repeated for WT1.

Progression free survival, duration of response and overall survival (as defined in Section 2.2) will be estimated using the method of Kaplan and Meier for each group. Survival estimates will be presented with 90% confidence intervals. These endpoints will also be compared between the CML patients and controls using log-rank tests.

Progression free survival for CML patients is defined in Section 2.2 and is measured as the time from date of consent to the study to date of progression or death from any cause. Alive patients who are progression free will be censored at their date of last follow up. Similar analysis will be performed for overall survival and duration of response.

Toxicity will be collected and evaluated according to the NCI CTC toxicity scale (v4.0) and compared between the vaccinated and control groups by Fisher's exact test.

10.2.2 ANALYSIS FOR AML PATIENTS ONLY:

Primary:

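### The 39 AML patients in the go rule must have data to 8 weeks (synopsis) or 16 weeks (section 3), and with replacement allowed the text does not settle whether an early relapse or death counts among them

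*Protocol*

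**What the plan says.** **Minimum data.** The synopsis states that "39 patients with data to at least 8 weeks will be recruited into the AML treatment group". Section 3 gives the same number, 39, but as "HLA A2 +ve patients with data to at least 16 weeks will be recruited into the AML treatment group". The 32 CML patients carry the same pair of conditions. In both places the HLA A2-negative controls are simply all who are eligible and consent, with no minimum-data condition.

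**Replacement.** Section 3.1 says that where patients are not eligible for analysis under section 10.2, "additional patients may be recruited in their place". Section 4.4 is firmer and says that non-evaluable patients will be replaced.

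**Analysis sets.** Section 10.2 requires two post-baseline time points for molecular response, testing to at least week 8 for immune response and at least one dose for vaccinated patients in the safety analysis. It then says: "For all other analyses, an intention to treat principle will be used". AML PFS falls under that last sentence.

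**Endpoint and drop-out.** Section 10.2.2 measures AML PFS from consent to relapse or death. Section 10.1.2 needs at least 16 of 39 patients alive without relapse at 2 years and adds: "The drop-out rate is expected to be less than 10% (see section 3.1 for details of patient replacement"). For CML, section 10.1.1 inflates 32 for drop-out, "hence a total of 36 patients will be recruited", but gives a pass mark only for 32.

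**The concern.** The go rule compares a count among 39 patients with a null 2-year PFS of 30% measured from consent. That comparison is valid only if the 39 are also counted from consent. If a patient must have data to week 8 or 16 to be one of the 39, and a patient without them may be replaced, an early relapse or death can leave the denominator. The observed rate then becomes a rate among patients who were still progression free at that week, and it is judged against a threshold that carries no such condition.

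The condition would also apply to the vaccinated arm alone, so the log-rank comparison with the controls would contain guaranteed event-free time on one side.

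The primary AML decision is at stake. A choice between the two readings made once outcomes are known could decide whether 16 of 39 is reached.

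**Working it through.** **Inputs (section 10.1.2).** Null PFS 30%, target PFS 50%, n = 39, pass mark 16. The false-positive risk is fixed for "a treatment that has a true PFS rate 30%) is set at 10"% and the false-negative risk for "a treatment with a true PFS rate of 50%) is set at 10"%. The protocol gives no hazard shape. A constant hazard is my assumption and is varied below.

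**Step 1: the plan's own figure.** Take the smallest n and r with P(X ≥ r | n, 0.30) ≤ 0.10 and P(X ≥ r | n, 0.50) ≥ 0.90, using exact binomial tails. The result is n = 39, r = 16, as stated.
- False-go rate: P(X ≥ 16 | 39, 0.30) = 9.4%
- Power: P(X ≥ 16 | 39, 0.50) = 90.0%

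These hold if all patients are counted from consent, as intention to treat implies.

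**Step 2: all failures before week t are replaced.** With a constant hazard, S(t) = 0.30^(t/104) under the null. The 2-year rate among those who remain is 0.30/S(t), and the false-go rate is P(X ≥ 16 | 39, 0.30/S(t)).

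| Reading | S(t) | Rate among the rest | False-go |
|---|---|---|---|
| Intention to treat, none replaced | 1 | 30.0% | 9.4% |
| 8 weeks, all earlier failures replaced | 0.912 | 32.9% | 18.1% |
| 16 weeks, all earlier failures replaced | 0.831 | 36.1% | 31.4% |

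Counting 104.36 weeks in 2 years instead of 104 gives 31.3% in the last row.

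**Step 3: cap at the drop-out ceiling.** If 10% of patients are removed and all are early failures, the null rate is 0.30/0.90 = 33.3%, and P(X ≥ 16 | 39, 0.333) = 19.6%.

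**Step 4: hazard shape.** Replace the constant hazard by a Weibull, S(t) = exp[ln(0.30) × (t/104)^k]. A shape k below 1 means that failures come early.

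| k | 8 weeks | 16 weeks |
|---|---|---|
| 0.7 | 33.9% | 58.5% |
| 1.0 | 18.1% | 31.4% |
| 1.3 | 12.9% | 19.7% |
| 1.5 | 11.4% | 15.9% |

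**Step 5: CML (null 5%, target 20%).**
- 4 of 32: alpha 7.4%, power 90.7%. The plan's figure reproduces.
- 4 of 36: alpha 10.4%, just above the 10% limit.
- 5 of 36: power 87.3%, below 90%.

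**The case against.** The strongest reply is that the operative text already protects the AML endpoint. Section 3.1 ties replacement to section 10.2, not to the 8- or 16-week phrase, and section 10.2 puts AML PFS under intention to treat. A patient who relapses at week 6 is then analysed and cannot be replaced. Relapse or death is itself the endpoint, so that patient's outcome is fully observed. Section 9 intends follow-up to 36 months and survival data for everyone, section 4.4 keeps data already collected on patients who withdraw consent, and sections 11.2 and 11.4 keep patients given alternative treatment in follow-up and analysis.

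Much of this stands. It is the better reading of sections 3.1 and 10.2, and under it nothing is inflated. It does not close the question. Under intention to treat no AML patient is ineligible for PFS, so the reference in section 10.1.2 to replacement for drop-out would replace nobody. It has effect only if some evaluability condition applies, and the only ones attached to the 39 are the two conflicting ones. No section says how an early relapse or death counts against them.

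Three stronger readings are tempting, and the protocol does not support them:
- *Evaluability is defined in four conflicting ways.* The two-test rule and intention to treat serve different endpoints and do not conflict. The two-test rule also follows from a response definition that needs two consecutive samples. The contradiction is 8 against 16 weeks, and the poor fit of both with section 10.2.
- *The false-go rate of the plan is 31%.* That needs the 16-week phrase to override sections 3.1 and 10.2, replacement of every earlier failure, and a constant hazard.
- *Without replacement, power falls to 74%.* P(X ≥ 16 | 39, 0.45) = 74.4% takes the full 10% loss and counts every loss as a failure. Section 10.1.2 expects less than 10%, and section 10.2.2 censors such patients. This is a worst case.

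**Conclusion.** The point holds as an unresolved contradiction about who makes up the denominator of the primary AML decision. It does not show that the stated design has the wrong error rates: 16 of 39 reproduces exactly, and under intention to treat it delivers 9.4% and 90.0%.

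The conditional size is a false-go rate of about 18% under the 8-week phrase or 31% under the 16-week phrase, if all earlier failures are replaced and the hazard is constant. Under the 10% drop-out ceiling it is about 20%. Hazard shape alone moves the 16-week figure between 15.9% and 58.5% over the shapes tried, so no single value should be quoted as the effect. Every replacement scenario shown exceeds the 10% limit, and most come close to doubling it or more. That is reason enough to remove the ambiguity before results are known.

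The CML part is minor. Thirty-six is 32 inflated for drop-out (32/0.9 = 35.6), and a pass mark for 32 evaluable patients is coherent. The protocol only lacks the pass mark for a different number analysed.

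**What to change.** - Delete the 8-week condition from the synopsis and the 16-week condition from section 3, for both diseases.
- State in sections 3.1, 4.4 and 10.1.2 that every consented, eligible HLA A2-positive AML patient counts in the go-rule denominator from consent. A patient who relapses or dies early counts as a failure and is not replaced. The denominator should not start at first vaccination: PFS runs from consent, and failures before the first dose would again be lost in one arm only.
- Make the replacement wording in sections 3.1 and 4.4 agree (may against will), and limit it to analyses for which section 10.2 sets an evaluability condition.
- For CML, keep the molecular set of section 10.2, and state the pass mark for the number actually analysed with its exact alpha and power.

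The single-stage rule itself needs no change. The cost is one amendment of wording. The only downside is that observed rates may be slightly less favourable than if early failures were replaced.

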3.1 PATIENT EVALUABILITY AND REPLACEMENT

Where patients do not fulfil the necessary criteria to be eligible for analysis (as set out in Section 10.2) additional patients may be recruited in their place.

4 SELECTION AND WITHDRAWAL OF PATIENTS

4.1 INCLUSION CRITERIA

CML patients:

Philadelphia chromosome positive CML in chronic phase, in complete cytogenetic response (CCyR) but with detectable BCR-ABL transcripts and maintained the CCyR on tyrosine kinase inhibitor monotherapy for a minimum of 24 months

AML patients:

Patients with WT1+ AML complete remission (CR) post chemotherapy or AML in morphologic CR with incomplete blood count recovery (CRi) defined as patients who fulfil all of the criteria for CR except for residual neutropenia (<1,000/ μ L) or thrombocytopenia (<100,000/ μ L).

As the vast majority of AML express WT and evaluation in CR or CRi is technically not feasible, formal demonstration of WT1 expression in AML cells is not required. Where historical or relapsed samples become available, WT1 expression status will be evaluated post hoc.

All patients:

- ≥ 18 years of age,
- Written informed consent
- WHO Performance status of 0 or 1.
- For vaccination groups: HLA-A0201 positive in at least one allele
- For control groups: HLA A2 negative in both alleles
- Renal function and liver function (Creatinine <1.5 x upper limit of normal, liver function tests < 1.5 x upper limit of normal); Lymphocyte count 
> 1.0 x10⁹/l*; normal clotting
- HB>100 g/l
- Adequate venous access for repeated blood sampling according to protocol schedule.
- If sexually active and possibly fertile, patients must agree to use appropriate contraceptive methods during the trial and for six months afterwards.

* If the lymphocyte count is below 1.0 at the time of entry into the trial but has been over 1.0 in the last 6 months and has also not declined rapidly in the days and weeks preceding entry, then the patient is eligible.

4.2 EXCLUSION CRITERIA

CML patients:

- CML in accelerated phase or blast crisis or having achieved CMR at any point during tyrosine kinase inhibitor therapy
- Tyrosine kinase inhibitor change or dose modification in the previous year, therapy interruption for more than 15 days in the previous 6 months to enrolment
- Prior interferon-α therapy
- Hypocellular bone marrow (<20%) (indicated by blood counts and most recent bone marrow (where available)
- Complete molecular response (CMR)

AML patients:

- AML in haematological relapse or eligible for allogeneic SCT.
- Hypocellular bone marrow (<20%)
- AML patients with the "good-risk" abnormalities comprised by the core binding factor leukaemias (i.e., AML with the translocation (8;21) and inversion of chromosome 16, and acute promyelocytic

leukaemia with the translocation (15;17))

All patients:

- Systemic steroids or other drugs with a likely effect on immune competence are forbidden during the trial. The predictable need of their use will preclude the patient from trial entry. Inhaled steroids are allowed.
- Major surgery in the preceding three to four weeks from which the patient has not yet recovered.
- Patients who are of high medical risk because of non-malignant systemic disease, as well as those with active uncontrolled infection.
- Patients with any other condition which in the Investigator's opinion would not make the patient a good candidate for the clinical trial, such as concurrent congestive heart failure or prior history of New York Heart Association (NYHA) class III/ IV cardiac disease
- Current malignancies at other sites, with the exception of adequately treated basal or squamous cell carcinoma of the skin. Cancer survivors, who have undergone potentially curative therapy for a prior malignancy, have no evidence of that disease for five years and are deemed at low risk for recurrence, are eligible for the study.
- Patients who are serologically positive for or are known to suffer from Hepatitis B, C, Syphilis or HIV. Counselling will be offered to all patients prior to testing.

4.3 **REGISTRATION PROCEDURE**

All registration and baseline assessments should be completed prior to registration.

Only patients fulfilling the eligibility criteria should be registered, any queries should be discussed with the University of Southampton Clinical Trials Unit before registration

All patients must be registered via the University of Southampton Clinical Trials Unit on:

[contact]

The patient's eligibility will be checked during the registration process. Eligible patients will be allocated a unique patient trial ID by the University of Southampton Clinical Trials Unit.

4.4 WITHDRAWAL CRITERIA

Patients who are removed from the study treatment due to adverse experiences (clinical or laboratory) will be treated and followed according to accepted medical practice. All pertinent information concerning the outcome of such treatment must be recorded in the CRF.

Patients who withdraw their consent from participating in the trial will be withdrawn from protocol procedures. Data that has been collected on these patients to this timepoint will be included in the analyses.

The discontinuation of study treatment will occur under the following circumstances

- Unacceptable toxicity
- Any patient who experiences a WHO CTC grade 3 adverse reaction (AR), possibly or likely to be related to vaccination will discontinue further vaccination.
- Severe local toxicity (CTC 3 or greater) at the site of injection, development of clinically relevant anti-DNA antibodies or rheumatoid factors, clinical or biochemical evidence of muscle destruction (CTC 3 or greater) or other unexpected toxicity will lead to termination of the vaccination of that patient.

- Unforeseen events: any event which in the judgement of the Investigator makes further treatment inadvisable
- SAE requiring discontinuation of treatment
- The patient withdraws consent where a patient is not evaluable, additional patients will be recruited to replace them (See Section 3.1)
- Serious violation of the study protocol (including persistent patient attendance failure and persistent non-compliance)
- Evidence of disease progression
- In patients with CML requirement to discontinue or change the dose of tyrosine kinase inhibitor therapy

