5.4 DOSE MODIFICATIONS, REDUCTIONS AND DOSE DELAYS

There will be no dose reductions or dose modifications.

Haematological toxicity – If patients experience CTC toxicity >2, vaccination will not be administered. Further vaccination may be offered after normalization if appropriate in the opinion of the treating clinician and only after documented discussion with the UoSCTU and lead investigators. Severe local toxicity (CTC 3 or greater) at the site of injection, development of clinically relevant anti-DNA antibodies or rheumatoid factors, clinical or biochemical evidence of muscle destruction (CTC 3 or greater) or other unexpected toxicity will lead to termination of the vaccination of that patient.

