7.1.8 OTHER SYSTEMIC TOXICITY

Haematological toxicity: It is possible that vaccination with WT1 may cause cytopaenias in patients who have a hypocellular low marrow reserve (hypocellular bone marrow). This is because WT1 is also expressed at low levels in normal CD34+ stem cells. To minimise the possibility of this, we will exclude patients with low marrow reserve (bone marrow cellularity <20%). Patients who develop cytopaenia will be treated with 5 days of intravenous methylprednisone (1-2 mg/kg). This steroid treatment will not start for 2-3 weeks after the start of cytopaenia to allow time to determine if cell counts rebound. They will also be given supportive care including blood products, growth factors and antibiotics as clinically indicated until the counts recover. The development of other systemic toxicity appears unlikely. FBC, biochemistry, in particular renal function and clinical AE will be assessed by CTC criteria.

• If CTC toxicity >2 occurs in a particular patient, vaccination will be paused. Further vaccination may be offered after normalization if appropriate in the opinion of the treating clinician and only after documented discussion with the UoSCTU and lead investigators.

Cardiac or renal toxicity: It is possible but from the available dataset in the literature unlikely, that the patients may develop immune related toxicity that affects the kidney or cardiac function. Patients will therefore have regular monitoring of their renal function, including urine sampling for proteinuria, and an ECG before any vaccination dose is given. Additional tests will be undertaken as clinically indicated, should signs of renal or cardiac dysfunction occur.

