8.3.3 SERIOUS ADVERSE EVENTS AND REACTIONS

Fatal or life threatening SAEs and SUSARs should be reported within 24 hours of the local site becoming aware of the event. The SAE/SUSAR form asks for nature of event, date of onset, severity, corrective therapies given, outcome and causality (i.e. unrelated, unlikely, possible, probably, definitely). The responsible investigator should assign the causality and expectedness of the event with reference to the current IMP IB and use the event terms and grades given in the NCI CTCAE v4.0. Additional information should be provided as soon as possible if the event/reaction has not resolved at the time of reporting.

Relapse and death due to CML or AML, and hospitalisations for elective treatment of a pre-existing condition do not need reporting as SAEs.

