8.3.6 SARS NOT REQUIRING IMMEDIATE REPORTING

The most recent Investigator Brochure (IB) for the IMPs being used in this trial will be circulated to participating centres by the UoSCTU and is to be stored in the local site file.

Side effects and toxicities that are expected are listed in the IB do not require immediate reporting in this trial, unless they are of an unexpected severity.

Death as a result of disease progression and other events that are primary or secondary outcome measures are also not considered to be SAEs.

SAEs of the above types should be recorded on the SAE/SUSAR form provided and this should be forwarded to the UoSCTU in a timely manner.

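### Protocol 4.4 ends vaccination for a vaccine-related grade 3 haematological or systemic reaction that 5.4 and 7.1.8 only pause, and 8.3.6 exempts outcome-measure events from SAE status against 8.1, 8.3.3 and 8.3.4

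*Protocol*

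**What the plan says.** **Vaccination after toxicity.** Protocol 4.4 (Withdrawal criteria) lists among the grounds for stopping study treatment: "Any patient who experiences a WHO CTC grade 3 adverse reaction (AR), possibly or likely to be related to vaccination will discontinue further vaccination". It gives no route back to vaccination.

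Protocol 5.4, under haematological toxicity, says "If patients experience CTC toxicity >2, vaccination will not be administered" and then "Further vaccination may be offered after normalization if appropriate in the opinion of the treating clinician", subject to documented consultation of the trials unit and the lead investigators. Protocol 7.1.8 (Other systemic toxicity) says "If CTC toxicity >2 occurs in a particular patient, vaccination will be paused" and repeats the restart provision with the same condition.

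For severe local toxicity, clinically relevant anti-DNA antibodies or rheumatoid factors, and muscle destruction, 4.4 and 5.4 carry the same sentence, ending "or other unexpected toxicity will lead to termination of the vaccination of that patient".

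**What counts as an SAE.** Protocol 8.3.6 says: "Death as a result of disease progression and other events that are primary or secondary outcome measures are also not considered to be SAEs". Its next sentence reads in part: "SAEs of the above types should be recorded on the SAE/SUSAR form provided"; the form is to be forwarded without undue delay, but no number of hours is given. Protocol 8.3.3 has a narrower exemption: "Relapse and death due to CML or AML, and hospitalisations for elective treatment of a pre-existing condition do not need reporting as SAEs". Protocol 8.1 makes any event that results in death serious, and 8.3.4 requires a form for all SAEs and SUSARs within 24 hours.

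**The concern.** A site that sees a possibly related grade 3 cytopenia finds one section that ends vaccination and two that allow it to restart. Whether such a patient goes on to further doses then depends on which section is consulted, so later exposure to the vaccine is not fixed by the protocol.

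The SAE wording raises a similar problem. An exemption defined by the endpoint list grows with that list, and here the list includes survival and toxicity. A non-disease death or a serious toxicity could then be handled outside the 24-hour route that 8.3.4 prescribes for all SAEs.

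An analysis plan cannot repair either point, because both govern what sites do and report.

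**Working it through.** No figure in the plan bears on this, so the check sets the texts side by side.

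**Part 1: end or pause**

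| Section | Trigger | Causality test | Consequence | Restart |
|---|---|---|---|---|
| 4.4 | grade 3 reaction | possibly or likely related | vaccination ends | none given |
| 5.4 (haematological) | CTC toxicity above 2 | none | dose withheld | possible after normalization and central consultation |
| 7.1.8 (other systemic) | CTC toxicity above 2 | none | vaccination paused | same as 5.4 |

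1. Toxicity above grade 2 judged unrelated meets only the pause rule, so there is no conflict.
2. Severe local toxicity, muscle destruction and relevant autoantibodies end vaccination in both 4.4 and 5.4, so there is no conflict between those two sections.
3. A grade 3 haematological or other systemic reaction judged possibly or likely related meets the trigger in 4.4 and also the one in 5.4 or 7.1.8. The consequences differ.
4. The pause rule cannot be confined to unrelated events. Section 7.1.8 opens by explaining that WT1 vaccination might itself cause cytopaenia, and neither 5.4 nor 7.1.8 excludes related events.

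Population under these rules: 32 CML + 39 AML = 71 vaccinated patients, or 36 + 39 = 75 with the CML recruitment total in 10.1.1. Each is planned to receive up to 6 + 6 = 12 vaccinations (5.2).

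**Part 2: SAE scope**

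1. Section 8.3.6 exempts events that are primary or secondary outcome measures.
2. Section 2.2 lists overall survival and CTCAE toxicity as secondary endpoints in both CML and AML. The AML primary endpoint in 10.2.2 counts death from any cause.
3. Combining 1 and 2, the literal wording covers deaths not due to leukaemia and serious toxicities.
4. Section 8.1 makes death a seriousness criterion without exception. Section 8.3.3 exempts three things only: relapse, death due to CML or AML, and elective hospitalisation for a pre-existing condition. Section 8.3.4 sets 24 hours for all SAEs. The result of step 3 conflicts with all three sections.
5. Section 8.3.6 is also inconsistent within itself: it says these events are not SAEs, then calls them SAEs and requires the SAE/SUSAR form.
6. Another sentence of 8.3.6 waives immediate reporting of expected toxicities listed in the investigator's brochure unless their severity is unexpected. Section 8.3.4 makes no such exception, so this sentence needs reconciling too.

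**The case against.** **On part 1.** The triggers differ, because 4.4 requires a causal link and the other two sections do not. Many cytopenias here may be judged unrelated: AML patients can enter with incomplete count recovery (4.1), and CML patients stay on a tyrosine kinase inhibitor (5.6). This narrows the overlap but does not remove it, since 7.1.8 is written with vaccine-caused cytopaenia in view.

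A reader might also infer that every vaccine-related grade 3 reaction is governed by conflicting rules, or that a site may restart vaccination on its own. Neither is supported: 4.4 and 5.4 share the same termination sentence for local toxicity, muscle destruction and autoantibodies, and a restart needs documented central consultation. Nor would the recorded toxicity data necessarily differ by site, since the event is graded and reported whichever rule is followed (8.3, 8.3.2). What can differ is later exposure.

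**On part 2.** A reader might infer that the protocol declares no death and no toxicity to be an SAE, or that such events go unreported. No sentence says so. That reading comes from combining 8.3.6 with 2.2, and it would make the sentence on expected toxicities of unexpected severity pointless. The narrower list in 8.3.3 is probably what was meant. The events also still reach the trials unit on the SAE/SUSAR form. This objection largely stands as to intent, but the wording still contradicts three other sections on SAE status and timing.

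A further inference would be that the DMEC or the trial-level stop is put at risk. Section 12.1 has the DMEC review safety listings at regular intervals and the trial management group review listings every 2 to 3 months. It does not make the 24-hour form the DMEC's source. Under 12.1, a second life-threatening vaccine-related case leads to discussion of termination. A delayed stop is therefore speculative.

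**Conclusion.** Both contradictions hold, within limits.

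1. A vaccine-related grade 3 haematological or other systemic reaction ends vaccination under 4.4 and may be followed by further vaccination under 5.4 or 7.1.8.
2. The literal wording of 8.3.6 removes SAE status and the 24-hour clock from non-disease deaths and serious toxicities, against 8.1, 8.3.3 and 8.3.4. It does not remove reporting altogether. Under 8.3.5 the SAE duty runs to 4 weeks after the last study drug, which bounds the period concerned.

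The vaccination rules apply to about 71 to 75 patients. The documents give no expected rate of related grade 3 reactions or of non-disease deaths, so the number of events affected cannot be stated. Part 1 assumes that the pause rule includes related events, as the opening of 7.1.8 indicates. Part 2 assumes that sites may apply 8.3.6 as worded rather than as probably intended. This should be corrected by amendment. It does not threaten the primary analyses, and no view is taken here on which clinical rule is right.

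**What to change.** 1. Reconcile 4.4, 5.4 and 7.1.8 so that one rule applies to vaccine-related toxicity above grade 2. The clinical team decides which rule that is.
2. In 8.3.6, delete the clause that exempts primary and secondary outcome measures. Align the remaining exemption with the full list in 8.3.3: relapse, death due to CML or AML, and elective hospitalisation for a pre-existing condition.
3. Reconcile the 8.3.6 sentence on expected toxicities listed in the investigator's brochure with the 24-hour rule for all SAEs in 8.3.4. Deleting the outcome-measure clause alone would leave that conflict in place.

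The cost is amendment wording, a notice to sites, and probably a few more expedited reports. Sample size, endpoints and analyses do not change.
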